7.5 Reporting of study treatment errors including misuse/abuse

Medication errors are unintentional errors in the prescribing, dispensing, administration or monitoring of a medicine while under the control of a healthcare professional, patient or consumer (EMA definition).

Misuse refers to situations where the medicinal product is intentionally and inappropriately used not in accordance with the protocol.

Abuse corresponds to the persistent or sporadic, intentional excessive use of a medicinal product, which is accompanied by harmful physical or psychological effects.

Study treatment errors and uses outside of what is foreseen in the protocol will be collected in the DAR (dose administration record) eCRF irrespective of whether or not associated with an AE/SAE and reported to Safety only if associated with an SAE. Misuse or abuse will be collected and reported in the safety database irrespective of it being associated with an AE/SAE.

Table 7-2 Guidance for capturing the study treatment errors including misuse/abuse

Treatment error type	Document in Dose Administration (DAR) eCRF (Yes/No)	Document in AE eCRF	Complete SAE form
Unintentional study treatment error	Yes	Only if associated with an AE	Only if associated with an SAE
Misuse/Abuse	Yes	Yes	Yes, even if not associated with a SAE

7.6 Pregnancy reporting

To ensure patient safety, each pregnancy occurring after signing the informed consent must be reported to Novartis within 24 hours of learning of its occurrence. The pregnancy should be followed up to determine outcome, including spontaneous or voluntary termination, details of the birth, and the presence or absence of any birth defects, congenital abnormalities, or maternal and/or newborn complications.

[figure not shown]
Pregnancy must be recorded on the Pharmacovigilance Pregnancy Form and reported by the investigator to the local Novartis DS&E Department. Pregnancy follow-up should be recorded on the same form and should include an assessment of the possible relationship to the study treatment.

Any SAE experienced during the pregnancy and unrelated to the pregnancy must be reported on a SAE form.

8 Data review and database management

8.1 Site monitoring

Before study initiation, at a site initiation visit or at an investigator’s meeting, a Novartis representative will review the protocol and data capture requirements (i.e. eCRFs) with the investigators and their staff. During the study, Novartis employs several methods of ensuring protocol and Good Clinical Practice (GCP) compliance and the quality/integrity of the sites’ data. The field monitor will visit the site to check the completeness of patient records, the accuracy of data capture / data entry, the adherence to the protocol and to Good Clinical Practice, the progress of enrollment, and to ensure that study treatment is being stored, dispensed, and accounted for according to specifications. Key study personnel must be available to assist the field monitor during these visits. Continuous remote monitoring of each site’s data may be performed by a centralized Novartis CRA organization. Additionally, a central analytics

organization may analyze data & identify risks & trends for site operational parameters, and provide reports to Novartis Clinical Teams to assist with trial oversight.

The investigator must maintain source documents for each patient in the study, consisting of case and visit notes (hospital or clinic medical records) containing demographic and medical information, laboratory data, electrocardiograms, and the results of any other tests or assessments. All information on eCRFs must be traceable to these source documents in the patient's file. The investigator must also keep the original informed consent form signed by the patient (a signed copy is given to the patient).

The investigator must give the monitor access to all relevant source documents to confirm their consistency with the data capture and/or data entry. Novartis monitoring standards require full verification for the presence of informed consent, adherence to the inclusion/exclusion criteria, documentation of SAEs, and of data that will be used for all primary variables. Additional checks of the consistency of the source data with the CRFs are performed according to the study-specific monitoring plan. No information in source documents about the identity of the patients will be disclosed.

8.2 Data collection

The trial will be conducted in a fully validated Data Capture system which conforms to US CRF 21 Part 11 requirements. Investigator site staff will not be given access to the system until they have been trained. Designated investigator staff will enter the data required by the protocol into the Data Capture system. Automatic validation programs within the system check for data discrepancies in the eCRFs and by generating appropriate error messages, allow the data to be confirmed or corrected by the investigator staff. The investigator staff must certify that the data entered are complete and accurate. After database lock, the investigator will receive copies of the patient data for archiving at the investigational site.

8.3 Database management and quality control

Novartis staff (or contract research organization [CRO] working on behalf of Novartis) review the data entered into the eCRFs by investigational staff for completeness and accuracy and instruct the site personnel to make any required corrections or additions. Queries are sent to the investigational site using an electronic data query. Designated investigator site staff is required to respond to the query and confirm or correct the data. If the electronic query system is not used, a paper Data Query Form will be faxed to the site. Site personnel will complete and sign the faxed copy and fax it back to Novartis staff that will make the correction to the database. The signed copy of the Data Query Form is kept at the investigator site.

Concomitant medications entered into the database will be coded using the World Health Organization (WHO) Drug Reference List, which employs the Anatomical Therapeutic Chemical classification system. Concomitant procedures, non-drug therapies and adverse events will be coded using the Medical dictionary for regulatory activities (MedDRA) terminology.

Laboratory samples will be processed centrally and the results will be sent electronically to Novartis (or a designated CRO).

Randomization codes and data about all study drug(s) dispensed to the patient and all dosage changes will be tracked using an Interactive Response Technology (IRT). The system will be supplied by a vendor, who will also manage the database. The database will be sent electronically to Novartis (or a designated CRO).

Each occurrence of a code break via IRT will be reported to the clinical team and monitor. The code break functionality will remain available until study shut down or upon request of Novartis.

The occurrence of relevant protocol deviations will be determined. After these actions have been completed and the database has been declared to be complete and accurate, it will be locked and the treatment codes will be unblinded and made available for data analysis. Any changes to the database after that time can only be made after written agreement by Novartis Development management.

8.4 Data monitoring committee

An established program level Data Monitoring Committee (DMC) independent of Novartis that reviews safety data from LCZ696 studies will be used for this study. The DMC will review SAEs in an unblinded manner on a regular basis and determine if it is safe to continue the study. Any major recommendation from the DMC will be communicated to the Executive Committee and must be reviewed and ratified by the Executive Committee in consultation with Novartis prior to its enactment.

The membership of the DMC and the responsibilities of the DMC and Novartis will be defined in a separate document entitled the "Data Monitoring Committee Charter". The DMC Charter will include information about data flow, purpose and timing of DMC meetings, guidance in the decision making process, communication strategy, procedures for ensuring confidentiality, procedures to address conflicts of interest and statistical monitoring guidelines.

8.5 Adjudication committee

Angioedema adjudication committee

If an angioedema or angioedema-like event occurs, the investigator will complete an Adjudication Questionnaire for an Angioedema-like Event form (provided by Novartis). Details on the process of reporting angioedema and angioedema-like events are outlined in a manual provided to investigators.

Submission of an angioedema report is not a substitution for the submission of an SAE report. If an angioedema-like event satisfies the definition of an SAE, the investigator must submit an SAE report in addition to the Adjudication Questionnaire for an Angioedema-like Event.

The membership and responsibilities of the Angioedema Adjudication Committee are defined in a separate document that will be provided to the sites. The project-level angioedema adjudication committee will be used for this trial.

9 Data analysis

The analysis will be conducted on all subject data at the time the trial ends. Any data analysis carried out independently by the investigator should be submitted to Novartis before publication or presentation.

9.1 Analysis sets

The following analysis sets will be used for the statistical analyses:

The full analysis set (FAS) will consist of all randomized patients with the exception of those patients who have not been qualified for randomization and have not received study drug, but have been inadvertently randomized into the study, and the exception of those patients who have been inadvertently randomized within a wrong stratum (ACEi, ARB, No RASi) and have not received study drug. Following the intent-to-treat principle, patients will be analyzed according to the treatment to which they were assigned at randomization. Efficacy variables will be analyzed based on the FAS as the primary set.

The safety (SAF) set will consist of all randomized patients who received at least one dose of study drug. Patients will be analyzed according to the treatment actually received. The SAF will be used for the analyses of safety variables.

The per protocol set (PPS) will be a subset of the FAS which will consist of the patients who do not have major deviations from the protocol procedures in the randomized treatment epoch. Major protocol deviations will be pre-specified prior to unblinding treatment codes for analyses. This supplemental efficacy set will be used to support the primary analysis results.

9.2 Patient demographics and other baseline characteristics

Baseline value is defined as the last non-missing assessment prior to the first dose of randomized study drug unless specified otherwise.

Summary statistics will be provided by treatment group for demographics and baseline characteristics, including age, age group (<65 years vs. ≥65 years; <75 years vs. ≥75 years), sex, race, ethnicity, weight, height, body mass index (BMI), category of prior CV medication, prior HF hospitalization, NYHA class, NT-proBNP, BNP, and vital signs. BMI will be calculated as weight (kg) / height² (m²) from the collected height and weight at Visit 1 (screening). Continuous variables will be summarized using n, mean, standard deviation, median, minimum, and maximum. Categorical variables will be summarized using frequencies and percentages.

The FAS will be used for the above analyses.

9.3 Treatments

The overall duration on the randomized study drug will be summarized by treatment group using mean, standard deviation, median, minimum, and maximum. Additionally, the number and percentage of patients will be summarized by treatment group for duration category. Mean doses and dose levels will be summarized by treatment group and visit.

Concomitant medications and significant non-drug therapies, prior to and after the randomization date respectively, will be summarized by therapeutic class, preferred term, and treatment group for the SAF.

The number and percentage of patients on different CV background medications (eg mineralocorticoid receptor antagonist, β -blockers, diuretics, and digoxin) will be tabulated by treatment at baseline and during the randomized treatment epoch.

The FAS will be used for the above analyses unless otherwise specified.

9.4 Analysis of the primary variables

The primary objectives are to demonstrate that LCZ696 is superior to individualized medical therapy for comorbidities in reducing NT-proBNP from baseline after 12 weeks of treatment, and/or in improving exercise capacity as assessed by the 6MWT at Week 24 in a subset of patients with B6MWD ranging from 100 meters to 450 meters.

9.4.1 Primary variables

The primary efficacy variables are the change from baseline in log(NT-proBNP) at Week 12, and the change from baseline in six-minute walk distance (6MWD) at Week 24.

For patients who have died, the 6MWD after the death will be defined as zero.

For patients who permanently discontinue from study treatment, assessment values collected after permanent discontinuation will generally be included in the analysis.

9.4.2 Statistical model, hypothesis, and method of analysis

Testing strategy

The following primary null hypotheses will be included in the testing strategy.

- H_1 : LCZ696 is no better than the comparator in change from baseline in log(NT-proBNP) at Week 12 in the overall study population
- H_2 : LCZ696 is no better than the comparator in change from baseline in 6MWD at Week 24 in patients with B6MWD ranging from 100 meters to 450 meters.

The following secondary null hypotheses will be included in the testing strategy.

- H_3 : LCZ696 is no better than the comparator in change from baseline in KCCQ CSS at Week 24 in the overall study population.
- H_4 : LCZ696 is no better than the comparator in NYHA change from baseline at Week 24 in the overall study population.

Each null hypothesis is tested against the one-sided alternative that LCZ696 is better than the comparator in the corresponding variable.

In order to control the family-wise type-I error rate at the one-sided 0.025 significance level, a sequentially rejective multiple testing procedure based on the graphical presentation ([Bretz et al 2009](#)) will be employed, whereby H_1 and H_2 will be tested first at initially assigned level of one-sided $(9/10) \times \alpha = 0.0225$ and one-sided $(1/10) \times \alpha = 0.0025$, accordingly. If H_1 and/or H_2 are rejected, the alpha for the rejected null hypotheses will be propagated to H_3 , such that, H_3

[figure not shown]
will be tested at the updated alpha level (one-sided 0.025 if both H_1 and H_2 are rejected; one-sided 0.0225 if H_1 is rejected but H_2 is not rejected; one-sided 0.0025 if H_2 is rejected but H_1 is not rejected); if H_3 is rejected, the alpha will be propagated to H_2 or H_4 based on the initial step rejection status.

- With H_1 rejected but H_2 not rejected at the initial step, if H_3 is rejected at one-sided 0.0225, the alpha will be propagated to H_2 , such that, H_2 will be tested again at one-sided 0.025; if H_2 is rejected at one-sided 0.025, the alpha will be further propagated to H_4 . Otherwise, the testing procedure will stop.
- With H_2 rejected but H_1 not rejected at the initial step, if H_3 is rejected at one-sided 0.0025, the alpha will be propagated to H_4 , such that, H_4 will be tested at one-sided 0.0025. Otherwise, the testing procedure will stop.
- With both H_1 and H_2 rejected at the initial step, if H_3 is rejected at one-sided 0.025, the alpha will be propagated to H_4 , such that, H_4 will be tested at full alpha (one-sided 0.025). Otherwise, the testing procedure will stop.

Figure 9-1 provides graphical illustration of the sequentially rejective testing procedure.

Figure 9-1 Graphical illustration of the sequentially rejective testing procedure

Based on the above testing procedure, if applicable, H₁, H₂ and H₃ will be tested based on the corresponding MMRM models (Section 9.4.2, Section 9.5.1.1), H₄ will be tested based on the longitudinal proportional cumulative odds model (Section 9.5.1.3)

If statistical significance had been established in the mean difference in change from baseline to Week 24 for KCCQ CSS, the following responders will be analyzed accordingly, based on the longitudinal binary logistic regression models (Section 9.5.1.1), to further illustrate the clinical relevance of the observed differences in terms of proportion of responders.

- KCCQ CSS improvement (defined by at least 5 points improvement);
- KCCQ CSS deterioration (defined by at least 5 points deterioration);

No multiplicity adjustment will be done for these supportive responder analyses (i.e., the tests for the responder analyses will be performed at nominal level of one-sided 0.025).

NT-proBNP analyses

The changes from baseline in log(NT-proBNP) will be analyzed using a mixed model for repeated measures (MMRM), in which, the response variable will be the changes from baseline in log(NT-proBNP); stratum (defined by prior ACEi/ARB medication usage [ACEi, ARB, None]), region, treatment (LCZ696, individualized medical therapy), visit and treatment-by-visit interaction will be included as fixed-effect factors; baseline log(NT-proBNP), stratum-by-baseline and visit-by-baseline interactions will be included as covariates; the within-patient covariance will be modeled using an unstructured covariance matrix (a common matrix for the two treatment groups). The analysis will include all post-baseline scheduled visits up to Week 12 (Week 4, Week 12) and will be performed based on the likelihood method with an assumption of missing at random (MAR) for missing data (Siddiqui et al 2009, National Research Council 2010).

Based on the MMRM model, the primary null hypothesis, H_1 , will be tested based on the testing strategy, the estimates and the two-sided 95% confidence intervals will be provided for the adjusted geometric means for the ratio to baseline in NT-proBNP at Week 12 in each of the two treatment groups (LCZ696 and individualized medical therapy), and for the ratio of the adjusted geometric means (LCZ696 over individualized medical therapy).

The FAS will be used for the above primary analyses.

As a supportive analysis, the same approach will also be performed on the PPS.

6MWD analyses

The changes from baseline in 6MWD will be analyzed using a MMRM model, in which, the response variable will be the changes from baseline in six-minute walk distance; stratum (defined by prior ACEi/ARB medication usage [ACEi, ARB, None]), region, treatment (LCZ696, individualized medical therapy), visit and treatment-by-visit interaction will be included as fixed-effect factors; baseline six-minute walk distance (B6MWD), baseline systolic blood pressure (BSBP), stratum-by-B6MWD, stratum-by-BSBP and visit-by-B6MWD interactions will be included as covariates; the within-patient covariance will be modeled using an unstructured covariance matrix (a common matrix for the two treatment groups). The analysis will include all patients with B6MWD ranging from 100 meters to 450 meters, and all post-baseline scheduled visits up to Week 24 (Week 16 and Week 24), and will be performed based on the likelihood method with an assumption of MAR for missing data (other than due to death).

Based on the MMRM model, the primary null hypothesis, H_2 , will be tested based on the testing strategy, the estimates and the two-sided 95% confidence intervals will be provided for the adjusted means for the change from baseline in 6MWD at Week 24 in each of the two treatment groups (LCZ696 and individualized medical therapy), and for the adjusted mean difference (LCZ696 minus individualized medical therapy) at Week 24.

All patients in the FAS with B6MWD ranging from 100 meters to 450 meters will be used for the above primary analysis.

As a supportive analysis, the same approach will also be performed on the FAS with all patients included, regardless of B6MWD values, and on the PPS.

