- With H2 rejected but H1 not rejected at the initial step, if H3 is rejected at one-sided 0.0025, the alpha will be propagated to H4, such that, H4 will be tested at one-sided 0.0025. Otherwise, the testing procedure will stop.
- With both H1 and H2 rejected at the initial step, if H3 is rejected at one-sided 0.025, the alpha will be propagated to H4, such that, H4 will be tested at full alpha (one-sided 0.025). Otherwise, the testing procedure will stop.

Figure 2-1 provides graphical illustration of the sequentially rejective testing procedure.

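### When 6MWD, KCCQ and NYHA are rejected but NT-proBNP is not, 0.0025 of alpha is left unused after H4; passing it to H1 is a small improvement that takes nothing from any other test

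*Protocol*

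**What the plan says.** Protocol 9.4.2 (Testing strategy) sets its aim as "In order to control the family-wise type-I error rate at the one-sided 0.025 significance level". H1 (NT-proBNP, Week 12) starts with 0.0225 and H2 (6MWD, Week 24) with 0.0025. Whatever is rejected passes its alpha to H3 (KCCQ CSS). After H3, "the alpha will be propagated to H_2 or H_4 based on the initial step rejection status". H1 is not among the destinations. Three branches follow:

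- **H1 rejected, H2 not.** If H3 is rejected at 0.0225, "such that, H_2 will be tested again at one-sided 0.025", and H4 follows if H2 is then rejected.
- **H2 rejected, H1 not.** "With H_2 rejected but H_1 not rejected at the initial step, if H_3 is rejected at one-sided 0.0025", alpha moves to H4, "such that, H_4 will be tested at one-sided 0.0025. Otherwise, the testing procedure will stop". Nothing is said about what happens once H4 is rejected.
- **Both rejected.** H3 and then H4 are tested at 0.025.

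SAP 2.5.2 repeats the second branch ("rejected but H 1 not rejected at the initial step") with the same levels and the same end point. SAP section 4 reports no change from the protocol.

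**The concern.** The two primary hypotheses are treated differently. H2 gets a second test at the full level if the rest of the sequence succeeds. H1 does not, and neither document gives a reason. In the H2-first branch H4 is the last hypothesis, so the 0.0025 it releases has no other use in the plan.

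At stake is a narrow case: the one-sided NT-proBNP p-value lies between 0.0225 and 0.025, and 6MWD, KCCQ CSS and NYHA are each significant at 0.0025. The confirmatory claim on NT-proBNP is then lost, although the declared error rate would allow it.

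**Working it through.** **1. Inputs (Protocol 9.8, repeated in SAP 3).** 2500 patients randomized 1:1, so 1250 per arm.

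| Endpoint | Effect | SD | Evaluable per arm |
|---|---|---|---|
| NT-proBNP | 11% to 24% reduction | 0.81 (log scale) | 1250 × 0.90 = 1125 |
| 6MWD | 22 to 30 m | 120 m | 1250 × 0.90 × 0.88 = 990 |
| KCCQ CSS | 2 to 3 points | 15.52 | 1250 × 0.95 = 1187.5 |
| NYHA | improved 14% vs 19%, worsened 6% vs 5% | n/a | 1187.5 (5% dropout assumed; none is stated) |

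**2. The plan's own power figures.** Power = Φ(effect / (SD × √(2/n)) − z), with z = 2.0047 at 0.0225, 1.9600 at 0.025 and 2.8070 at 0.0025.

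- NT-proBNP, 11%: −ln(0.89) = 0.1165; 0.1165 / 0.03415 = 3.412; Φ(3.412 − 2.005) = 0.920 (stated 92%).
- 6MWD, 22 m at 0.0025: Φ(4.079 − 2.807) = 0.898 (stated 90%). At 30 m: 0.997 (stated 99%).
- KCCQ CSS, 2 points at 0.0225: Φ(3.140 − 2.005) = 0.872 (stated 87%). At 3 points: 0.997 (stated 99%).
- NYHA, ordinal Wilcoxon at 0.025: 0.902 (stated 90%).

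**3. What the written rules imply.** I took the text as a graph with initial weights 0.9 and 0.1; H1 to H3; H2 to H3; H3 to H2 first and to H4 only once H2 is gone. I then worked out the local levels for all 15 intersection hypotheses. Fourteen use the full 0.025. The exception is H1 alone, tested at 0.0225.

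**4. Adding a step from H4 to H1.** The level for H1 alone becomes 0.0225 + 0.0025 = 0.025. The other 14 intersections do not change. The validity argument needs no simulation, because the new step is reached only after H2, H3 and H4 have all been rejected:

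- If any of those three is a true null, a family-wise error has already occurred, and re-testing H1 adds none.
- If all three are false, only H1 can be a true null, and it is rejected only when p ≤ 0.025.

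Family-wise error is therefore at most 0.025 under any correlation. The step comes last, so it cannot alter a decision on H2, H3 or H4. A simulation with H1 null and the other three certain to be rejected gave about 0.0225 without the step and about 0.025 with it.

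**5. Ceiling on the gain.** This is the chance that the H1 p-value falls between 0.0225 and 0.025: Φ(δ − 1.9600) − Φ(δ − 2.0047), where δ = −ln(1 − reduction) / 0.03415.

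| NT-proBNP reduction | Ceiling (percentage points) |
|---|---|
| 11% | 92.68 − 92.04 = 0.64 |
| 13% | 0.20 |
| 15% | 0.04 |
| 17.5% | 0.002 |
| 24% | about 2 × 10⁻⁸ |

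Over all effect sizes the maximum is 1.8 points, at δ = 1.98. That is a reduction of 1 − exp(−1.98 × 0.03415) = 6.5%, below the planned range.

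**6. Expected gain at an 11% reduction.** The ceiling is multiplied by the chance that H2, H3 and H4 are all significant at 0.0025. With independent endpoints:

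- 6MWD 22 m, KCCQ 2 points: 0.898 × 0.630 × 0.672 × 0.64 = 0.24 points.
- 6MWD 30 m, KCCQ 3 points: 0.997 × 0.971 × 0.672 × 0.64 = 0.42 points.

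The documents give no correlation between endpoints. Over an assumed common correlation of 0 to 0.6, the first figure runs from 0.24 down to 0.07 and the second from 0.42 down to 0.19.

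**The case against.** The strongest reply is that nothing is broken. The plan promises control of family-wise error at one-sided 0.025 and delivers it; falling below the ceiling in one configuration is allowed, and a sponsor need not use every bit of alpha. That stands, so this can only be an optional improvement. A reader might infer that the testing procedure is invalid or inflates error; the written rules show the opposite, since they are conservative for H1.

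A reader might also infer that the trial would count as having missed its primary objective. The documents do not support that. Protocol 9.4 frames the primary objectives as NT-proBNP and/or 6MWD, and in this branch 6MWD has already been rejected at 0.0025. The two-sided 95% interval for the NT-proBNP ratio and its one-sided p-value are reported in any case, and with p below 0.025 that interval excludes 1. Only the formal claim on the second primary is lost.

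Two further objections stand in part:

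- **The figures.** The graphs in Figures 9-1 and 2-1 are not visible in the text available. It cannot be said that they lack an arrow from H4 to H1, only that the written rules, which agree in both documents, give no such step.
- **Cost.** The Amendment 2 rationale says the strategy was agreed with major health authorities, and Protocol 11.1 requires a written, approved amendment for any change. The change is free in alpha and power, but not in administration.

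One objection does not carry. The alpha left after H4 could go to SF-36 PCS instead, but SF-36 is outside the testing strategy. As the plan stands H4 is the end of the line, and sending its alpha to H1 displaces nothing.

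**Conclusion.** The point holds as a minor inefficiency. In the H2-first branch, once H3 and H4 are rejected, 0.0025 is unused and H1 remains at 0.0225. The procedure is dominated by one that adds a final re-test of H1 at 0.025: that version makes every rejection the present one makes, sometimes one more, within the same error limit.

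The benefit is small. At the bottom of the planned NT-proBNP range it is about 0.1 to 0.4 percentage points of H1 power, and over most of that range it is close to nil. The expected gain rests on the plan's effect sizes and SDs, an assumed 5% dropout for NYHA, and an assumed correlation of 0 to 0.6. The error-control argument rests on none of these.

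**What to change.** Before unblinding, extend the second bullet of the testing strategy in Protocol 9.4.2 and SAP 2.5.2: if H4 is rejected at one-sided 0.0025, the alpha is propagated to H1, which is re-tested at one-sided 0.025. Check Figures 9-1 and 2-1. If they lack an arrow of weight 1 from H4 to H1, add it; if they already have one, the sentence brings the text into line. If a hypothesis such as SF-36 PCS is ever placed after H4, its alpha should pass on to H1 in the same way.

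No patients are needed and no hypothesis loses level or power. The cost is a documented amendment and renewed contact with the health authorities that agreed the strategy. For a gain this small, it is best included in an amendment that changes the multiplicity section for another reason.
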